2.5.1 Primary endpoint(s)

The primary endpoint of the study is Major Molecular Response (MMR) achieved at week 48 while on study treatment (asciminib 40 mg b.i.d. and asciminib 80 mg q.d.). A subject will be counted as having achieved MMR at week 48 if he/she meets the MMR criterion (BCR::ABL1 \leq 0.1% IS) at week 48 while on study treatment.

MMR will be considered as a binary variable with subjects achieving MMR grouped as 'responders' and subjects not achieving MMR grouped as 'non responders'. Only subjects with MMR at 48 weeks are considered responders. In other words, any subject who achieves MMR before 48 weeks, but is no longer in MMR at 48 weeks, will be considered as a non-responder in this primary analysis.

Details of derivation of Polymerase Chain Reaction (PCR) results and calculation of BCR::ABL ratio are presented in [Section 5.4](#)

2.5.2 Statistical hypothesis, model, and method of analysis

The primary estimand will be analyzed based on the data from the FAS and according to the Intention-To-Treat (ITT) principle. Exact test for single proportion will be used at the one-sided 2.5% level of significance.

The null hypothesis is that the MMR rate at Week 48 is equal to 0.23. The alternative hypothesis is that the rate is greater than 0.23.

$H_0: \pi=0.23$ vs. $H_1: \pi >0.23$

where π is the major molecular response (BCR::ABL1 \leq 0.1% IS) rate at Week 48. MMR rate and its 95% confidence interval based on the Clopper-Pearson method will also be presented.

The null hypothesis will be rejected when the lower bound of the two-sided 95% CI is above 23%.

Summary statistics of MMR at week 48 will also be presented by randomized groups.

2.5.3 Handling of intercurrent events

The approach of accounting for intercurrent events is as follows:

- **For the intercurrent events 4a:** The composite strategy will be applied for treatment discontinuation due to any reason. Treatment discontinuations due to any reason will be defined as non-responders.
- **For the intercurrent events 4b:** The treatment policy strategy will be applied. Meaning, the actual values of the variable (BCR::ABL1 % IS) will be used, regardless of whether the intercurrent event has occurred.
- **For the intercurrent events 4c:** The treatment policy strategy will be applied. Meaning, the actual values of the variable (BCR::ABL1 % IS) will be used, regardless of whether the intercurrent event has occurred.

2.5.4 Handling of missing values not related to intercurrent event

Subjects with missing PCR evaluations at 48 weeks will be considered as non-responders. However, if the 48-week PCR evaluation is missing, but both a PCR evaluation at 36 weeks and a PCR evaluation at 60 weeks indicate MMR, the 48-week assessment is imputed as a 'Response', assuming that MMR is maintained between 36 and 60 weeks.

2.5.5 Sensitivity analyses

To explore the robustness of analysis, sensitivity analyses exploring different assumptions will be performed.

- The Exact test of MMR rate at 48 weeks will be repeated without any imputation (described in [Section 2.5.4](#)) used in the primary analysis in case of missing PCR evaluations at 48 weeks. If a subject has missing MMR at 48 weeks, then the subject will be considered as non-responder for primary analysis.
- As per the FDA guidelines "Statistical Considerations for Clinical Trials During the COVID-19 Public Health Emergency", in order to assess the impact of COVID-19 (including potential missing data) on the primary endpoint, the exact test of MMR rate at 48 weeks will be repeated on the FAS excluding the subjects with missing data at week 48 due to COVID-19. MMR rate and its 95% confidence interval based on the Clopper-Pearson method on the FAS excluding subjects with missing data at week 48 due to COVID-19 will also be presented.

2.5.6 Supplementary analyses

The FAS will be used for subgroup analyses.

Subgroup analyses of the primary efficacy endpoint to assess the homogeneity of the treatment effect across demographic and baseline disease characteristics may be conducted on the following subgroups, if there are enough subjects in each category:

- Gender: Male and Female
- Race: Asian, Caucasian, or others

- Age at baseline (≥ 18 -< 65 years, ≥ 65 years, ≥ 75 years)
- Reason for discontinuation of the last prior TKI: Warning or failure (i.e. lack of efficacy) or intolerance (i.e. adverse event, lack of tolerability) to the most recent TKI therapy at the time of screening

Note: Only one reason for discontinuation is allowed for each prior therapy.

- Number of prior TKI therapies: 2, 3 or ≥ 4
- Cytogenetic response status at baseline: Major (MCyR) - 0 to 35% Ph+ metaphases; Complete (CCyR) - 0% Ph+ metaphases; Partial (PCyR) - >0 to 35% Ph+ metaphases; Minor (mCyR) - >35 to 65% Ph+ metaphases; Minimal - >65 to 95% Ph+ metaphases; or None - >95 to 100% Ph+ metaphases.
- Prior TKI treatment: imatinib, nilotinib, dasatinib, bosutinib, radotinib or ponatinib
- Prior ponatinib: Yes or No
- Mutation status at baseline: Non-mutant or mutant

For the subjects with dose escalation to 200 mg q.d. after week 48, the MMR rate and its 95% confidence interval based on the Clopper-Pearson method at week 96 and week 144 will be presented based on FAS.

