6.1 Study treatment

The investigational treatment for this study is asciminib (40 mg b.i.d. or 80 mg q.d. as assigned by IRT). Novartis will supply asciminib to the investigational site as 20 mg and 40 mg tablets.

In patients not achieving MMR at 48 weeks or losing the response (confirmed loss of MMR in two consecutive tests) after the week 48 assessment up to week 108, asciminib dose may be escalated to 200 mg q.d. if in the investigator's opinion the patient may benefit from the escalation. In addition, to participate in the dose escalation, there must not be any grade 3 or 4 toxicity while on therapy, or persistent grade 2 toxicity, possibly related to asciminib and unresponsive to optimal management.

Dose escalation may happen at next schedule visit upon receipt of BCR-ABL1 and **CCI** [REDACTED].

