6.6.2 Dose escalation

For patients not in MMR at 48 weeks or losing the response after the week 48 assessments up to week 108, a dose escalation to 200 mg q.d. may be considered for patients on 40 mg b.i.d. or 80 mg q.d., if in the investigator's opinion the patient may benefit from the escalation. In addition, there must not be any grade 3 or 4 toxicity while on therapy, or persistent grade 2 toxicity, possibly related to asciminib and unresponsive to optimal management.

Patients with dose reduction to 40 mg due to side effects may receive a dose escalation to 200 mg daily if the event requiring the dose reduction has disappeared and the patient has been treated at least 3 months on the standard dose of 80 mg.

CCI [REDACTED] will be performed in patients not reaching MMR at 48 weeks or patients losing the response after the week 48 assessments up to week 108, and for whom a dose escalation might benefit the patient, to identify potential BCR-ABL mutations that could confer resistance to asciminib. With the limited information on mutations no general treatment recommendations can be given for individual mutations.

Dose escalation may be performed at week 60 for patients not in MMR at week 48. For patients losing the response after week 48 up to week 108, dose escalation may be performed up to week 120 after confirmed loss of MMR in 2 consecutive tests and CCI [REDACTED] results are available.

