8.3.1.1 Molecular response

Molecular response (MR) will be assessed in all patients.

Levels of BCR-ABL1 transcripts will be determined by real-time quantitative PCR (RQ-PCR) testing of peripheral blood and analyzed centrally. Log reduction in BCR- ABL1 transcripts levels from the standardized baseline value, or the percent ratio of BCR-ABL1 transcripts versus control gene (ABL1) transcripts converted to a reference standard, international scale (IS) ([Hughes and Branford 2006](#)), will be calculated for each sample.

Major molecular response and related variables are defined as the following:

- Rate of MMR where MMR is defined as a ≥ 3.0 log reduction in BCR-ABL1 transcripts compared to the standardized baseline equivalent to ≤ 0.1 % BCR-ABL1/ABL1 % by IS as measured by RQ-PCR, confirmed by duplicate analysis of the same sample,
- Time to MMR defined as the time from the date of enrollment to the date of the first documented MMR,
- Duration of MMR defined as the time from the date of first documented MMR to the earliest date of loss of MMR, progression to AP or BC, or CML-related death.
- Rate of Deep Molecular Responses MR4 and MR4.5 are defined as a ≥ 4 log or ≥ 4.5 log reduction in BCR-ABL1 transcripts compared to the standard baseline equivalent to 0.01 % or 0.0032% BCR-ABL1/ABL by IS as measured by RQ-PCR, confirmed by duplicate analysis of the same sample with at least 10,000 or 32,000 ABL1 transcripts, respectively.

Loss of MMR is defined as increase of BCR-ABL1/ABL to $> 0.1\%$ by international scale (IS) in association with a ≥ 5 -fold rise in BCR-ABL1 from the lowest value achieved on study

treatment and replicated by a second analysis of the same sample. Loss of MMR confirmed by subsequent sample analysis within 4 to 6 weeks showing loss of MMR associated with a ≥ 5 -fold rise in BCR-ABL1 from the lowest value achieved on study treatment, unless it is associated with confirmed loss of CHR or loss of CCyR or progression to AP/BC or CML-related death. The blood samples will be taken as described in [Table 8-1](#) and [Table 8-2](#).

If at one visit the sample is missing during transit to the central PCR laboratory, or the PCR result is difficult to interpret or sample not analyzable, or if the PCR sample was not collected, a subsequent unscheduled visit sample must be collected within 4 weeks either at the next scheduled visit (week 4 or week 8) or as an unscheduled visit.

Table 8-2 Blood samples (efficacy primary endpoint)

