Sample Type	Volume	Visit
Blood for BCR-ABL1 quantification by RQ-PCR	20 mL	Screening/Baseline
	20 mL	Week 12
	20 mL	Week 24
	20 mL	Week 36
	20 mL	Week 48
	20 mL	Every 12 weeks thereafter up to week 132 (w60, w72, w84, w96, w108, w120, w132)
	20 mL	End of Treatment

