1.1 Study design

The study is an international, multi-center, non-comparative, phase IIIb, treatment optimization study of asciminib (randomized 1:1 to either 40 mg b.i.d. or 80 mg q.d.) in adult subjects previously treated with 2 or more TKIs. 156 subjects will be randomized to either asciminib 40 mg b.i.d. or 80 mg q.d. An additional 30 subjects (randomized to either asciminib 40 mg b.i.d. or 80 mg q.d.) intolerant only to last TKI and in MMR at baseline will also be included.

Randomization is only used to have a balance in the allocation of treatment into either asciminib 40 mg b.i.d. or 80 mg q.d. The trial will not be powered to compare both treatments.

In subjects not achieving MMR at 48 weeks or losing the response after the week 48 assessment up to week 108, asciminib dose may be escalated to 200 mg q.d. if in the investigator's opinion

the subject may benefit from the escalation. In addition, there must not be any grade 3 or 4 toxicity while on therapy, or persistent grade 2 toxicity, possibly related to asciminib and unresponsive to optimal management.

[figure not shown]
BCR::ABL1 and **CCI** results are required before increasing asciminib dose, therefore the dose escalation can occur at next scheduled visit upon results review of the prior visit. In subjects losing response after the week 48 assessment, the last possible time point to initiate the 200 mg dose will be the week 120 visit to ensure that efficacy and safety of the dose escalation can be sufficiently established during the remaining trial follow up period.

If a dose decrease is required, subjects will return to the initial dosing regimen (q.d. or b.i.d.) they were using before the dose increase which was considered tolerable. For this reason, if a subject escalates from 40 mg b.i.d. to 200 mg q.d., in case of a required dose decrease, use of 80 mg q.d. is not allowed and the subject will continue 40 mg b.i.d. asciminib.

All subjects will be treated for a maximum duration of 144 weeks.

The primary endpoint of the study is MMR at 48 weeks.

Figure 1-1 Study design

*Treatment assignment to 40 mg b.i.d. or 80 mg q.d. (1:1) will be done through Interactive Response Technology (IRT).

Three analyses are planned for this study, including the 48-week primary analysis, the 96-week analysis, and the End-of-Study-Treatment (EOsT) analysis. The timing when those analyses are conducted is summarized in Section 2.1.

No formal interim efficacy analysis is planned in this study.

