- Duration of MMR defined as the time from the date of first documented MMR to the earliest date of loss of MMR, progression to AP or BC, or CML-related death.
- Rate of Deep Molecular Responses MR4 and MR4.5 are defined as a ≥ 4 log or ≥ 4.5 log reduction in BCR::ABL1 transcripts compared to the standard baseline equivalent to 0.01 % or 0.0032% BCR::ABL1/ABL by IS as measured by RQ-PCR, confirmed by duplicate analysis of the same sample with at least 10,000 or 32,000 ABL1 transcripts, respectively.

Loss of MMR is defined as increase of BCR::ABL1/ABL to $> 0.1\%$ by international scale (IS) in association with a ≥ 5 -fold rise in BCR::ABL1 from the lowest value achieved on study treatment and replicated by a second analysis of the same sample. Confirmed loss of MMR by subsequent sample analysis within 4 to 6 weeks showing loss of MMR associated with a ≥ 5 -fold rise in BCR::ABL1 from the lowest value achieved on study treatment, unless it is associated with confirmed loss of CHR or loss of CCyR or progression to AP/BC or CML-related death.

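### The MMR rate after 200 mg escalation has no escalation baseline, so subjects already in MMR before 200 mg could act can be counted in it

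*SAP*

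**What the plan says.** **Analysis.** SAP 2.5.6 plans, "For the subjects with dose escalation to 200 mg q.d. after week 48, the MMR rate and its 95% confidence interval". The time points are weeks 96 and 144, the interval is the exact (Clopper-Pearson) one, and the subjects come from the FAS. It sets no baseline PCR, comparator, test or threshold.

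**Entry after no MMR at week 48.** Protocol 6.6.2: "Dose escalation may be performed at week 60 for patients not in MMR at week 48". One PCR result decides.

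**Entry after loss of response.** Protocol 6.1 asks for more: "losing the response (confirmed loss of MMR in two consecutive tests) after the week 48 assessment up to week 108". SAP 5.4.1 also requires a level above 0.1% with an at least 5-fold "rise in BCR::ABL1 from the lowest value achieved on study treatment and replicated by a second analysis of the same sample", and a later confirming sample.

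**Timing.** SAP 1.1: "therefore the dose escalation can occur at next scheduled visit upon results review of the prior visit". The last possible start is week 120.

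**Response.** MMR is at most 0.1% IS, "confirmed by duplicate analysis of the same sample" (Protocol 8.3.1.1). No second sample is needed.

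**Available samples.** Protocol Table 8-2 schedules PCR at week 48 and "Every 12 weeks thereafter up to week 132", so every possible escalation visit from week 60 to week 120 has one.

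**Baseline rules.** SAP 2.1.1 makes the first escalated dose the reference start date for escalation, but the only efficacy baseline it defines is the last assessment on or before randomization. SAP 2.7 splits key safety summaries into before and after escalation. No such split is planned for efficacy.

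**The concern.** On the week 48 route, entry and response use the same 0.1% cut-off. Entry rests on a single sample, and the sample taken at the escalation visit plays no part in the analysis. A subject at 0.12% at week 48, then 0.08% at weeks 60 and 96, counts as in MMR after escalation although the crossing came before 200 mg could act. Duplicate analysis of one tube limits assay error but not variation between samples.

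The second problem is timing. The week 96 rate covers everyone who escalated, including those who had not yet started 200 mg at week 96.

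Dose escalation is one of three topics under Protocol 1.2, and Protocol 12.3 leaves the escalation analyses to the SAP. SAP 2.5.6 contains the only escalation-specific efficacy analysis we found in the readable text. Readers will naturally take this rate as a measure of what 200 mg adds.

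**Working it through.** **The plan's own figures.** None is stated for the escalation analysis: no expected rate, number of escalators or PCR variability. The only design figure is for the primary test (156 subjects, 23% against 33%, one-sided 0.025). It reproduces: 47 responders needed, exact alpha 0.0241, power 0.801. It is not at issue here.

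**Step 1. Is the worked example within noise?** The fall from 0.12% to 0.08% is log10(0.12/0.08) = 0.18. The difference of two independent PCRs has SD √2 × SD: 0.14 for SD 0.10 and 0.28 for SD 0.20. A fall of this size is unremarkable.

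**Step 2. How often would it happen with no effect?** Assumptions, because the documents give none:
- Subject i has a constant true log10 level m_i, and each PCR is y = m_i + e, with independent normal e of the stated SD.
- Three distributions of m_i were used: normal with between-patient SD 0.7 or 1.0, centred so that 33% are in MMR at week 48 (the plan's alternative rate), and log-uniform from 0.001% to 100%.
- An entrant has -1 < y48 ≤ 0, i.e. >0.1% to 1%. All entrants are treated as escalated at week 60.

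Simulated results, ranging over the three distributions:

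| Within-patient SD (log10) | P(y96 ≤ -1), entrants | P(y60 ≤ -1), entrants | P(y96 ≤ -1), entrants with y60 > -1 |
|---|---|---|---|
| 0.10 | 5-6% | 5-6% | 3% |
| 0.20 | 11% | 11% | 6-7% |
| 0.30 | 16-17% | 16-17% | 10-11% |
| 0.35 | 18-19% | 18-19% | 12-13% |

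The second and third columns agree because, with no effect or trend, weeks 60 and 96 are exchangeable.

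**Step 3. Share at or below 0.1% at both visits.** With a the week 96 (and week 60) figure and b the restricted figure, the share is a - (1 - a)b. At SD 0.20 (normal, 0.7): 0.114 - 0.886 × 0.068 = 0.054, about 5% of entrants. Over the whole range it is about 3% to 10%.

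**Step 4. Confirmed-loss route.** For a subject in stable MMR (true level log-uniform, 0.01% to 0.1%), a false confirmed loss (two samples, each above 0.1% and at least 5-fold above the lowest of four earlier values) has probability below 0.1% for SD up to 0.2, and 0.9% at SD 0.3. Noise matters little here.

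**Step 5. Late escalation.** A subject in MMR at week 96, with loss at week 108 that is then confirmed, may escalate at week 120. This is a subject with dose escalation who is in MMR at week 96, so the rate as written counts an MMR that precedes 200 mg. For an escalation at week 96 itself, the week 96 PCR comes too early for 200 mg to have acted.

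**Step 6. Conflict with the data rule.** SAP 2.1.1 drops efficacy data after treatment failure, except for PFS and OS. SAP 5.4.4 counts as failure a level above 1% at week 48, no CCyR at week 48, and confirmed loss of MMR. Read literally, post-escalation MMRs can come almost only from week 48 entrants at >0.1% to 1% with CCyR, the group nearest the cut-off. Confirmed-loss subjects could contribute only MMRs recorded before their loss.

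**Step 7. What a baseline does not remove.** With an assumed decline of 0.1 to 0.3 log10 per 48 weeks on the unchanged dose (SD 0.20, between-patient SD 0.7), week 96 MMR with no escalation effect is 18% to 34% unrestricted and 11% to 25% restricted.

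**The case against.** The analysis is supplementary and descriptive, in a study declared non-comparative. It carries no test, and the SAP does not attribute the responses to 200 mg. Any uncontrolled response rate is positive under no effect, including the restricted one. Escalation is optional and needs the investigator's judgement and further results, so the number of subjects escalated just above 0.1% is unknown. All of this stands. It limits the weight of the point but does not explain why subjects in MMR before 200 mg could act belong in a rate described as following escalation.

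A reader might infer more than the documents support:
- *That all escalators enter on one PCR.* They do not: the loss route needs two tests and a 5-fold rise.
- *That subjects gain from having two chances, week 96 or week 144.* The SAP reports two separate rates, not that composite.
- *That false responses would also come in number from entrants at 1% to 10% at week 48.* Read literally, the treatment-failure rule removes their later PCRs.
- *That response must be confirmed on two consecutive samples.* That would depart from the trial's MMR definition, make this rate inconsistent with the other MMR rates, and lose any MMR first seen at week 144.

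**Conclusion.** The point holds for the week 48 route and for late escalations. Followed as written, SAP 2.5.6 can count subjects already at or below 0.1% at the escalation visit, and week 96 MMRs that predate 200 mg. That much comes from the text and needs no assumption.

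The size does rest on assumption. For a within-patient SD of 0.10 to 0.35 log10, constant levels and no drug effect, about 5% to 20% of week 48 entrants at >0.1% to 1% would be in MMR at week 96. An escalation baseline lowers this to about 3% to 13%. It reduces the bias without eliminating it, and late response on the unchanged dose may be the larger part of what remains. The documents do not support a claim that the planned rate will mislead by any particular amount, or that the trial's primary conclusion is affected.

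**What to change.** A cheap improvement to SAP 2.5.6:

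1. Define the escalation baseline as the last PCR on or before the first 200 mg dose, normally the escalation-visit PCR.
2. Restrict the denominator for MMR after escalation to escalated subjects above 0.1% IS at that PCR. Report those already at or below 0.1% separately, not as responders.
3. Count only PCRs taken after the first 200 mg dose, so that subjects escalating at or after week 96 are left out of the week 96 rate.
4. Present results by entry route, and add the log10 change from the escalation baseline.
5. Keep the trial's MMR definition. Response confirmed on a second sample may be shown as a sensitivity analysis (about 1% to 4% under the no-effect assumptions above, with the baseline restriction).
6. Reconcile this analysis with SAP 2.1.1 and 5.4.4, stating whether PCRs after treatment failure are used for escalated subjects.
7. State that the rate is uncontrolled and still includes late response that would have occurred on the unchanged dose. Showing non-escalated subjects not in MMR at week 48 alongside would help the reader.

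The cost is SAP wording and programming, since the samples are already scheduled. The downside is a smaller denominator and a lower, less favourable rate. No change to the clinical escalation rule is implied.

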1. ***pre-treatment period:*** from day of subject’s informed consent to the day before first administration of study treatment
2. ***on-treatment period:*** from date of first administration of study treatment to 30 days after date of last administration of study treatment (including start and stop date).
3. ***post-treatment period:*** starting at day 31 after last administration of study treatment.

If dates are incomplete in a way that clear assignment to pre-, on-, post-treatment period cannot be made, then the respective data will be assigned to the on-treatment period.

Safety summaries (tables, figures) on the corresponding Safety set include only data from the on-treatment period with the exception of baseline data which will also be summarized where appropriate (e.g. change from baseline summaries). In particular, summary tables for adverse events (AEs) will summarize only on-treatment events, with a start date during the on-treatment period. In addition, a separate summary for death will be provided.

However, all safety data (including those from the pre-treatment and post-treatment) will be listed and flagged as appropriate.

Efficacy summaries on the FAS and FAS 2 (apart from OS and PFS) include data from baseline up to either the last assessment on or before the End of Treatment (EoT) visit or before or on treatment failure, whichever is the earliest.

The efficacy assessments collected post-treatment failure or post-EoT visit are not included in any efficacy analyses (except for OS and PFS analyses). However, they will be listed and flagged as appropriate.

Windows for multiple assessments

Data such as molecular response, cytogenetic response collected over time (including unscheduled visits) will be summarized by scheduled time point. As subjects do not always adhere to the visit schedule, visits will be remapped according to visit windows defined in Tables 2-1 to Table 2-3 of this document to enable by-visit analysis. Only those protocol-defined visits will have the visit window defined. Each assessment (including the end of treatment assessment), either scheduled or unscheduled, will have a mapped visit assigned, as long as study day is available, according to the defined visit window up to the date with data included.

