2.6.2 Statistical hypothesis, model, and method of analysis

No statistical testing of secondary efficacy endpoints will be performed .

Molecular response at and by time points

- Molecular Response MMR rate at weeks 12, 24, 36, 72, 96 and 144
- MMR rate at week 48 for subjects with MMR at baseline
- Rate of MR4 and MR4.5 at weeks 12, 24, 36, 48, 72, 96 and 144
- Rate of BCR::ABL1 $\leq 10\%$ and $\leq 1\%$ at Weeks 12, 24, 36 and 48
- Rate of BCR::ABL1 $\leq 10\%$, BCR::ABL1 $\leq 1\%$, MMR, MR4 and MR4.5 by all-time points

Frequency and percentage of all molecular response categories (defined in [Appendix](#)) using FAS or FAS 2 will be presented for each time point.

For each endpoint above, the rate and the associated 95% confidence interval based on the Clopper-Pearson method will be presented. For the at-time-points summary, subjects discontinuing the treatment prior to a specific time point due to any reason or subjects without an available assessment at that time point will be considered as non-responders for that time point. For the by-time-points summary, subjects without any documented response for which an evaluable response assessment was never provided will be considered as non-responders for the period of time up to that time point.

The cumulative incidence of MMR will be graphically displayed by an increasing step function. This curve will increase each time (after randomization) at which a new responder is observed and thus will increase up to the best observed response rate (e.g. up to 50% if half of the subjects in the analysis population are able to achieve response).

Additional chromosomal abnormalities and occurrence of high-risk ACAs

The number and percentage of subjects achieving MMR at week 48 and week 96, and CCyR at week 48 will be presented by ACA status at baseline. Per NCCN 2024 guideline and ELN 2020 guideline, the major route ACA/Ph+ including trisomy 8, isochromosome 17q, second Ph, trisomy 19, and chromosome 3 abnormalities are considered as presence of ACA at baseline.

Time to MMR

Time to MMR is defined in protocol Section 8.3.1.1 and calculated as: date of first documented MMR - date of randomization +1. Descriptive statistics (minimum, maximum, median, quartiles, mean, SD) of time to MMR will be provided.

The FAS will be also used to perform similar Time-to-Event analyses as described below for duration of MMR.

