5.4.4 Treatment Failure

In the event of treatment failure the subject should be discontinued from the study treatment. The ELN criteria 2020 do not make provisions for treatment failure in 3rd line however they define that a level of BCR::ABL1 $> 1\%$ IS and failure to achieve CCyR is not sufficient for optimal survival. The following events will constitute ‘treatment failure’:

- BCR::ABL1 $> 1\%$ IS at 48 weeks after initiation of therapy or no complete cytogenetic response at 48 weeks.
- Subject demonstrates new T315I mutation.
- Subject shows lack or loss of response such as “Loss of CHR, CCyR or PCyR at any time after initiation of therapy OR confirmed loss of MMR”.
- Progression to AP/BC.
- Subjects fulfilling treatment failure criteria above but without alternative treatment options may however be continued on study drug if in the investigators opinion they are obtaining benefit from the drug. Subjects with BCR::ABL 1 greater than 10%

after 48 weeks of treatment or subjects with signs of progression to AP and BC must however be discontinued.

- Subjects with newly emerging T315I mutation and lack or loss of response. While asciminib has known activity against CML with additional T315I mutation, the recommended dose of 200 mg bid for the treatment of T315I is not in use in the study. In case a subject demonstrates a new T315I mutation on asciminib, subjects should not continue in the study.

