5.5 Derivation of response rates and categories

5.5.1 Response rate at a specific time point

The molecular and cytogenetic response evaluations will be summarized by the following mutually exclusive categories which are based on the respective assessment within the time window:

- **Response categories** (sections 5.4.1 and 5.4.2): Subjects with an available assessment at that time point (+/- time window) indicating any of the response categories.
- **No response:** Subjects with assessment at that time point (+/- time window) indicating 'no response'
- **Missing:** Subjects without an evaluable response assessment at that time point (+/- time window). This category is then further split into subjects who are ongoing without treatment failure at the beginning of the relevant time window, subjects who are ongoing with treatment failure at the beginning of the relevant time window, subjects who discontinued due to lack of efficacy, disease progression (PD) or death and subjects who discontinued due to other reasons.

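### The MMR rate planned for subjects escalated to 200 mg (SAP 2.5.6) cannot count a 200 mg response in anyone who met an SAP treatment-failure criterion before escalating

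*SAP*

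**What the plan says.** The last paragraph of SAP 2.5.6 sets out the escalation analysis: "For the subjects with dose escalation to 200 mg q.d. after week 48, the MMR rate and its 95% confidence interval" (Clopper-Pearson) at Week 96 and Week 144, on the FAS. It gives no data rule or denominator rule of its own.

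The general data rule is in SAP 2.1.1: "The efficacy assessments collected post-treatment failure or post-EoT visit are not included in any efficacy analyses". Only OS and PFS are exempted. The excluded assessments are listed and flagged.

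SAP 5.4.4 defines treatment failure. Two of its criteria matter here:
- the Week 48 criterion, BCR::ABL1 above 1% "IS at 48 weeks after initiation of therapy or no complete cytogenetic response at 48 weeks";
- loss of response, described as "Loss of CHR, CCyR or PCyR at any time after initiation of therapy OR confirmed loss of MMR".

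Failure does not always end treatment: "Subjects fulfilling treatment failure criteria above but without alternative treatment options may however be continued on study drug", if the investigator sees benefit. Subjects above 10% after 48 weeks, or with signs of AP/BC, must stop.

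Protocol 6.6.2 gives two escalation routes. Patients not in MMR at Week 48 may escalate at Week 60. Patients who lose MMR later may escalate up to Week 120, once the loss is confirmed in two consecutive tests.

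**The concern.** Protocol 1.2 names benefit from escalation as one of the questions the study is meant to inform. Protocol Section 3 sets the last escalation visit at Week 120 so that efficacy and safety at 200 mg can still be established. Protocol 12.3 leaves analyses of escalated patients to the SAP. The rate in SAP 2.5.6 is the only visible efficacy summary specific to these subjects; disposition, safety and ECG summaries are planned separately.

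The general cut at treatment failure suits the response endpoints under the randomized regimen. For the escalation summary it works against the purpose, because meeting a failure criterion is often what makes escalation a question. The table could then show a low rate, or a rate in a selected subset, and be read as evidence on the 200 mg dose.

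**Working it through.** The plan states no figure for the escalation analysis, so there is none to reproduce. The primary calculation does reproduce: with 156 subjects and a 23% null, the exact test rejects at 47 or more responders (one-sided alpha 0.0241), and power at 33% is 80.1% against the stated 80%. Nothing below touches it.

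**Step 1. Trace each escalated subject through the rules.**

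| Status before first 200 mg dose | SAP 5.4.4 failure? | May stay and escalate? | 200 mg PCRs used under SAP 2.1.1? |
|---|---|---|---|
| Loss of MMR after Week 48, confirmed as in SAP 5.4.1 | Yes | Yes (Protocol 6.6.2) | No |
| Week 48 BCR::ABL1 >1%, or no CCyR | Yes | Only without alternatives; not if >10% or signs of AP/BC | No |
| Week 48 BCR::ABL1 >0.1-1%, with CCyR and no other criterion | No | Yes | Yes |

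Protocol 9.1.1 does not list loss of MMR alone as treatment failure, so the protocol does not take row 1 subjects off drug. The clash arises from the wider SAP list. A row 3 subject with no evaluable Week 48 marrow may move to row 2, because SAP 5.4.2 groups missing cytogenetics with non-responders unless the subject is in MMR.

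**Step 2. What happens to cut subjects in the rate.** SAP 2.5.6 is silent. SAP 5.5.1 has a Missing category with a split for "subjects who are ongoing with treatment failure at the beginning of the relevant time window". SAP 2.6.2, written for the secondary at-time-point rates, says "subjects without an available assessment at that time point will be considered as non-responders for that time point". There are therefore two possible treatments.

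Let s be the share of escalated subjects who are cut, p_c the 200 mg MMR rate among them, and p_u the rate among the rest. The true rate is (1 - s)p_u + s·p_c.
- Counted as non-responders: reported rate = (1 - s)p_u, a shortfall of s·p_c.
- Removed from the denominator: reported rate = p_u, a difference of s(p_u - p_c). This is zero if the groups respond alike, and an overstatement if cut subjects respond less.

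**Step 3. Illustration (s and p are assumed; the documents give neither).** Non-responder counting with p_u = p_c = p:

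| Assumed p | s = 25% | s = 50% | s = 75% |
|---|---|---|---|
| 20% | 15.0% | 10.0% | 5.0% |
| 25% | 18.75% | 12.5% | 6.25% |
| 30% | 22.5% | 15.0% | 7.5% |

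With 40 escalated subjects, p = 25% and s = 50%, the true 10/40 (25%, 95% CI 12.7-41.2) is reported as 5/40 (12.5%, 4.2-26.8). If the cut subjects leave the denominator instead, it is 5/20 (25%, 8.7-49.1), which describes only row 3 of the first table.

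**Step 4. The Week 96 time point.** SAP Table 2-1 counts from randomization. For Week 96 the window is day 96×7 - 40 = 632 to 96×7 + 43 = 715. Escalation at Week 108 (day 757) or Week 120 (day 841) falls after it. Weeks on 200 mg for an escalation visit v are max(0, 96 - v) and 144 - v:

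| Escalation visit | At Week 96 | At Week 144 |
|---|---|---|
| Week 60 | 36 | 84 |
| Week 72 | 24 | 72 |
| Week 84 | 12 | 60 |
| Week 96 | 0 | 48 |
| Week 108 | 0 | 36 |
| Week 120 | 0 | 24 |

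On scheduled visits, a loss seen at Week 84 leads to escalation at Week 96, a loss at Week 96 to Week 108, and a loss at Week 108 to Week 120. Only the last group can still be in MMR on 80 mg at Week 96. Each such subject adds 1/40 = 2.5 points to the Week 96 rate with 40 escalated subjects, or 1/20 = 5 points with 20. With the loss confirmed as in SAP 5.4.1, that subject's Week 144 PCR, after 24 weeks on 200 mg, is then cut. At the 96-week analysis, only subjects treated at least 120 - 96 = 24 weeks longer than the last one can have reached Week 120.

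**The case against.** The case on the other side is that this is one untested supplementary rate, that escalation is not a listed primary or secondary objective, and that some exploratory and biomarker text is redacted. Failed subjects should normally discontinue, escalation also needs investigator judgement and acceptable toxicity, and the excluded PCRs stay visible in listings. The non-responder rule in SAP 2.6.2 was not written for SAP 2.5.6, and Week 48 failures start further from MMR, so equal response rates may exaggerate the loss.

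Most of this limits the size and leaves the clash in place. Listings do not repair a rate. Loss-route subjects are not told by Protocol 9.1.1 to stop for loss of MMR alone. The lower response of Week 48 failures is already in the formula: the shortfall is s·p_c, which shrinks to zero as p_c does.

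Three stronger readings are tempting, and the documents do not support them:
- **That many or most escalated subjects are cut.** No count of escalated subjects, or of those already in failure, is given. The group at >0.1-1% with CCyR could be the majority.
- **That the rate is certainly biased down.** This needs the non-responder rule. Under the other denominator the rate is selective and could err upward.
- **That the date of the confirmatory sample decides whether a response counts.** SAP 5.4.1 says "Confirmed loss of MMR by subsequent sample analysis within 4 to 6 weeks showing loss of MMR", and PCRs are scheduled every 12 weeks, so one might infer that a loss confirmed at the next visit escapes the failure label. No text says the two consecutive tests may be 12 weeks apart. Protocol 8.3.1.1 uses the same 4 to 6 weeks, and Protocol 8.4.2 allows unscheduled draws to confirm loss.

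**Conclusion.** The point stands. Under SAP 2.1.1 and 5.4.4 as written, a 200 mg response cannot count in the SAP 2.5.6 rate for any escalated subject who first met an SAP failure criterion. This covers loss-route escalators whose loss is confirmed as the SAP defines it, and Week 48 failures who continue and escalate. The conclusion assumes that the general cut governs SAP 2.5.6, which is the natural reading since only OS and PFS are exempted.

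The size cannot be fixed from the documents. On the assumed inputs the shortfall runs from 5 points (p = 20%, s = 25%) to 22.5 points (p = 30%, s = 75%) under non-responder counting.

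The Week 96 timing effect is real but minor. A reader might infer broad inflation from all late escalators, but on scheduled visits it is confined to Week 120 loss-route escalators.

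The change should be made, because the summary cannot otherwise answer the escalation question for these subjects. No primary or confirmatory conclusion depends on it.

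**What to change.** Amend SAP 2.5.6 in three respects:

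1. State that the treatment-failure cut in SAP 2.1.1 does not apply to the MMR summary of escalated subjects.
2. Use on-treatment PCRs dated after the start date of dose escalation, which SAP 2.1.1 already defines.
3. Limit the Week 96 rate to subjects who started 200 mg before that assessment, or index the rate to weeks since escalation using the study-day reference already in SAP 2.1.1.

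A split by escalation route and an explicit rule for a missing PCR would help the reader but are optional.

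The cost is a few sentences and one reworked descriptive table. No new data are needed, since the PCRs are already scheduled every 12 weeks. The downside is small cells, so the table should carry no formal comparison.
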